2.6 RECRUITMENT OF PARTICIPANTS (SAMPLING)

School eligibility

Intervention status will be randomly assigned to 132 schools across the Schools Division of Zamboanga del Norte (ZDN) Province, resulting in 66 schools per arm.

To be eligible for the intervention and study, schools will need to meet a set of minimum inclusion criteria. This is intended to ensure that schools participating have the required infrastructure in place for the intervention to be effective. The minimum inclusion criteria will include:

- (i) Water for handwashing was available at the school for at least certain days of the week
- (ii) The overall pupil to toilet ratio equaled 100 or lower
- (iii) School has at least one individual or group handwashing station
- (iv) School is situated in a district deemed safe by DepEd²⁸
- (v) School does not have any planned WASH programming in the upcoming 2019-20 school year beyond standard WinS activities

We used data from DepEd's WinS Online Monitoring System (OMS) tsto assess the eligibility of public elementary schools. DepEd division offices collect this data via self-assessment by schools. Based on the alignment between initial observations from our scoping and piloting trip for the study and the OMS data, we believe this data is reliable. We can further confirm these assumptions with data from Research Question 2 (RQ2).

Based on the above, 210 out of 634 (33%) schools were eligible for random selection.

Randomization procedure

²⁸Within Zamboanga del Norte, DepEd has identified all school districts within Zone 1-3 and several in Zone 4, as sites for the study. DepEd excluded the remaining school districts within the division due to safety and accessibility concerns.

Schools were assigned to treatment or control group based on a two-step stratified randomization procedure. Stratification ensures the schools are balanced across relevant characteristics that may affect our outcome of interest. In our case, our strata were determined by the "WinS implementation quality index score" (WinS IQ). Each school was assigned a WinS IQ score using data from the OMS. These criteria capture whether schools have infrastructure conducive to our outcomes of interest. Scores ranged from 0 to 9 based on how many of the criteria they met, and was based on a series of nine sanitation, hygiene, and overall WASH indicators.²⁹

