We also determined variables in the OMS data that may indicate that the school has basic features which are conducive to the nudge intervention, or "nudge enabling" features. Specifically:

- No Information, Education, and Communications (IEC) campaign materials on hygiene in toilets or handwashing areas
- Toilets have lights

We categorized schools as having "nudge enabling" features based on whether a combination of these basic criteria were satisfied³⁰. We determined 114 schools had such features.

First, we randomly sampled 100 of these 114 "nudge enabled" schools. We randomly assigned 50 schools to treatment group and 50 schools to control group, stratifying by three categories of WINS quality index scores (Low 2-5, Medium 6-7, and High 8-9). Within our sample of 132 schools, we oversampled "nudge enabled" schools in an attempt to hold constant bathroom environments across schools in our evaluation sample. This was done out of the concern that substantial differences in bathroom environments at baseline (for instance, some more cluttered than others) may dilute the effect of nudges.

To achieve our final sample of 132 schools, 32 supplementary schools were randomly drawn from the 96 non-nudge enabler schools remaining in the eligible population. Again, half were randomly assigned to treatment group and half were randomly assigned to control group within each WiNS index strata to ensure balance on this key variable. Note, this was done in order to introduce variation in baseline handwashing environment, since we hypothesize this is an important mediator for the impact of nudges. This procedure aims to ensure that the nudges are installed in more environments likely to be conductive to them, as such environments would also be targeted in any scale-up decision.

However, we will not be comparing treatment effects in nudge-enabled and non-nudge-enabled schools. We constructed the "nudge-enabled" indicator only to identify schools more likely to have non-cluttered facilities, in order that we can select for a higher probability of non-cluttered classrooms during sampling, as such classrooms would likely be more conducive to the nudges. This indicator was created using available school-level administrative data. However, in our evaluation, we are ultimately interested in the effect of "clutteredness" at the handwashing facility-level (rather than the school-level) on the impact of the nudges. Therefore, rather than using our "nudge-enabled" constructed

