Potential spill-overs are expected to be minor, and would likely result in the treatment estimate being a lower bound of the impact of the program. The nudges intervention was randomly assigned at the school-level. Distances between schools within Zamboanga del Norte vary. Spillovers would occur when students from schools of different treatment statuses interact. For example, students from treatment schools who interact often with friends and family from control schools with lower handwashing rates may be influenced to was their hands less often than treatment students without such friends. Students may also transfer between schools of different assignment statuses during the study, such that a student from a treatment school may transfer into a control school and influence their new classmates to wash their hands more often. However, pupils are expected to attend schools closest to their homes, and to have friends who are also from their *barangay* (neighborhood) and who would attend the same school. Therefore, spillovers are unlikely to have a meaningful effect on the treatment estimates.

Representativeness and External Validity

We intend to generate evidence on the effectiveness of behavioral nudges to inform national scaleup plans in the Philippines, and to add to the global body of research on handwashing and behavioral change interventions.

The target population for the nudges intervention includes pupils in grades 1 to 6 in selected elementary schools in Zamboanga del Norte. It is important to note two ways in which these schools may differ from other schools in the Philippines. First, these schools are located in DepEd school divisions in which UNICEF has designated a priority target district for WinS programming. These areas are chosen because of high rates of poverty as well as particularly willing partners in the associated DepEd Division offices. Second, schools that were identified as eligible for the intervention, and were included in the evaluation sample, met minimum inclusion criteria related to the current WASH conditions and programs being implemented at these schools, as described in Section 2.5 Recruitment

Pre-analysis plan [DRAFT] | January 20, 2020

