of Participants (Sampling). It is important to keep in mind the characteristics of the schools participating, when considering how the evaluation findings may predict the impact of the intervention in other schools in the Philippines. However, it is also important to note that the intervention is intended for, and meant to be scaled up in, environments similar to those meeting our minimum inclusion criterial; that is, classrooms with minimum handwashing enablers such as facilities, water, and soap.

For outcomes based on pupil classroom observations, all grade 1-6 pupils at sample schools will be eligible for the evaluation sample frame, with the exception of pupils in classrooms where the only handwashing facility available to pupils when in class is not observable (only inside the toilet and not visible to surveyors), or there is no toilet for pupils to use inside or directly outside the classroom.

DIDINSIGHT DATA. DECISIONS. DEVELOPMENT.

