³⁴ The approach to test the difference in impact of the program for these two sub-samples will be separate regressions for each sub-sample and then a test comparing the treatment effects across the two regressions. This will be performed instead of a single regression on the pooled sample with an interaction term between the treatment term and the sub-sample for the sake of simplicity, as the former approach would require multiple interaction terms for all co-variates, as well as threeway interactions when exploring other sub-groups.

Note on sample weights: Sample weights will be included to account for the fact that the sampling probability of classes for a given grade is different across schools. Since a constant number of classes will be sampled for each grade in each school³⁵, schools with more classes for a given grade will have a lower probability of being selected. This will be accounted for by using weights that represent the inverse probability of class selection. By doing so, each pupil observed or surveyed will have the same probability of inclusion into the sample.

Table 3 below provides a summary of the indicators for this research question, and the unit of analysis and sample corresponding to each indicator. Table lists the co-variates we will use in addition to the indicators in our analytical models to answer research question 1. We will report estimates for our outcome indicators both with and without controls.

³⁵ For classroom observations, one class in each grade in each school will be sampled independent of the total number of classes in the grade.

Pre-analysis plan [DRAFT] | January 20, 2020

Outcome category	Outcome	Metric	Unit	Sample	Analytic model ³⁶ (LPM – linear probability model ; OLS – ordinary least squares)
Independen t	Pupil washed hands with soap and water after toilet use	Y.1 – binary variable for whether pupil was observed to wash hands with water and soap after toilet use	Pupil	Separately for: Grade 1-3 pupils Grade 4-6 pupils	LPM: Y = Y.1
handwashin g after toilet use	Pupil washed hands with water after toilet use	Y.1 – binary variable for whether pupil was observed to wash hands with water after toilet use at school	Pupil	Separately for: Grade 1-3 pupils Grade 4-6 pupils	LPM: Y = Y.1

Table 3: Outcome Indicators for Research Question 1

³⁶ Unless otherwise stated, the independent variable of interest is treatment assignment.

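### Does the weighting note's claim of equal inclusion probability for every pupil make the RQ1 estimate wrong or its population unclear?

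*SAP*

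**What the plan says.** In Section 6, Research Question 1, part 1.b, the note on sample weights begins correctly: the chance that a class is sampled differs between schools. Footnote 35 gives the rule: "one class in each grade in each school will be sampled independent of the total number of classes in the grade". The note then says that "schools with more classes for a given grade will have a lower probability of being selected", prescribes "weights that represent the inverse probability of class selection", and ends with "By doing so, each pupil observed or surveyed will have the same probability of inclusion into the sample".

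The population is described elsewhere. Section 4, under Representativeness and External Validity, says: "The target population for the nudges intervention includes pupils in grades 1 to 6 in selected elementary schools in Zamboanga del Norte". It adds that "all grade 1-6 pupils at sample schools will be eligible for the evaluation sample frame", apart from classrooms whose only handwashing facility cannot be observed and classrooms with no toilet inside or directly outside.

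Section 2.6 describes the school draw. After the eligibility screen, "210 out of 634 (33%) schools were eligible for random selection". Of these, 114 were classed as nudge-enabled and 96 were not. "First, we randomly sampled 100 of these 114" nudge-enabled schools, and 32 of the other 96 were added, with half of each group assigned to each arm within WinS score strata. The section says that the oversampling is deliberate, gives the reason, and notes that conducive settings are the ones a scale-up would target.

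**The concern.** Weights act in the estimator, after the sample has been drawn. They offset unequal inclusion and cannot make inclusion equal, so the closing sentence claims a property that the design lacks. The sentence about schools with more classes has a related slip. Schools were drawn by nudge-enabled status, not by number of classes. It is each class in such a school that has the lower chance.

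The possible harm is to interpretation. A reader told that every pupil had the same chance of inclusion might apply the pooled effect and handwashing rates to all 210 eligible schools. There the school draw was unequal, and the class weights do not correct it. Table 4 says that the impact may be greater in nudge-enabled schools, and Section 2.6 rules out comparing effects by that status, so a reader could not re-mix the result from the planned output. Levels matter too, because Section 2.5 ties a scale-up recommendation to rates above 15 percent.

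A further worry is that, if a fixed number of pupils is observed per class, class weights alone do not represent pupils in large and small classes equally.

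**Working it through.** **Counts.** The plan's figures agree with each other: 210/634 = 0.331 (stated as 33%), 114 + 96 = 210, and 100 + 32 = 132.

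**Class stage.** With K classes in a grade and one drawn, P(class) = 1/K and the weight is K.

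| K | P(class), weighted or not | Weight | Product |
|---|---|---|---|
| 1 | 1.00 | 1 | 1 |
| 2 | 0.50 | 2 | 1 |
| 3 | 0.33 | 3 | 1 |
| 4 | 0.25 | 4 | 1 |

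The second column shows that the sentence is wrong as worded. The last column shows that the weight is right. If all pupils in the drawn class are observed, each represents K pupils of that grade and school, and the weighted sample reproduces the pupils of the sample schools.

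**Illustration with assumed values.** Take three schools with (K, class size, effect) of (1, 20, 3 pp), (1, 45, 7 pp) and (4, 40, 12 pp).
- Pupil-population effect: (20×3 + 45×7 + 160×12)/225 = 10.2 pp.
- Class-weighted, whole class observed: 10.2 pp.
- Class-weighted, same number observed per class: (1×3 + 1×7 + 4×12)/6 = 9.7 pp.
- Unweighted, same number per class: (3 + 7 + 12)/3 = 7.3 pp.

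In this example the planned weight recovers the target under whole-class observation and most of the gap under a fixed number.

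**Within-class stage.** Section 2.5 lists 13 pupils per grade group. Split evenly over three classes (an assumption), that is 13/3 = 4.3 per class. At assumed class sizes of 25 and 50, the chance of being observed once the class is drawn is 17.3% and 8.7%. This would matter only if the 13 is an observation quota. Section 2.5 gives it as a sample-size input. Table 2 says that pupils are observed after they have used the toilet, so entry depends on toilet use, and Section 3.2 leaves further enumerator procedures to a separate guideline.

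**School stage.** Selection probabilities are 100/114 = 0.877 and 32/96 = 0.333, a ratio of 2.63. The nudge-enabled share is 100/132 = 0.758 of the sample and 114/210 = 0.543 of the eligible schools, a difference of 0.2147. With schools of equal size and before class weights:
- Shift in pooled effect = 0.2147 × (difference in effect between school types). Assumed differences of 2 and 5 pp give 0.43 and 1.07 pp.
- Shift in treated rate = 0.2147 × (effect difference + control-rate difference). With assumed control-rate differences of −2 to +2 pp, this runs from 0.2147 × (2 − 2) = 0.00 to 0.2147 × (5 + 2) = 1.50 pp.

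The documents give none of these differences, and every shift is zero if the school types do not differ.

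**Cost of a 210-school estimate.** School weights are 114/100 = 1.14 (100 schools) and 96/32 = 3.0 (32 schools). The Kish factor is 132 × (100×1.14² + 32×3²)/210² = 1.251, so the standard error rises by √1.251 = 1.118. With 66 schools per arm, 26 observations each, ICC 0.1 (design effect 1 + 25×0.1 = 3.5) and 10% against 17%, the standard error goes from 0.0217 to 0.0243 and power from 0.897 to 0.822. Class weights and unequal school sizes are left out, so the factor for the combined weight would differ.

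**The case for a change.** The strongest case for acting is that the sentence is false, the one before it names the wrong unit, and the note does not say whom the weighted estimate represents. Correction would take a few words. Section 2.5's planning figures put the treated rate at 10% + 7 pp = 17%, only 2 pp above the 15 percent line, and an assumed shift of up to 1.5 pp is not trivial against that margin.

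The literal error stands, and so does the arithmetic. The inference to a defect in the analysis does not.

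- The note's first sentence names the right unit and its prescription gives the right weight. An analyst who follows it computes the intended quantity.
- The population is stated in Section 4, with its exclusions and a warning about extrapolation. Repeating it in the weighting note would only be a cross-reference. A short label such as 'the 132 sample schools' would be less exact, because it drops the classroom exclusions and the allowance in Section 2.5 for schools that cannot be observed.
- The 1.5 pp is the extreme of an assumed range, and it measures distance from a mix of schools that the plan does not target. The scale-up decision concerns conducive settings.
- A 76:24 description counts schools. The mix behind a pupil-level weighted estimate depends on observations and class counts that the documents do not give.
- A within-class factor presupposes an observation quota that the SAP does not set.

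**Conclusion.** No change follows. The equal-probability sentence and the reference to schools instead of classes are clerical slips around a correct instruction. Setting them right would move no estimate, standard error, p-value or conclusion. Random assignment was balanced within each group of schools and the weighting rule is the same in both arms, so the treatment-control contrast is unbiased for the sample schools, which are the population the SAP names.

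The size is therefore zero for the planned estimand. For pupils of all 210 eligible schools, the effect would shift by about 0.21 pp per 1 pp difference between school types, or 0.4 to 1.1 pp for assumed differences of 2 to 5 pp. The plan does not set out to estimate that quantity, and estimating it would cost about 12% in standard error under the school-stage calculation. Oversampling conducive schools and reporting for the sample is a fair, disclosed trade-off.

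The conclusion assumes that the class weights are applied as the note prescribes and that the enumerator guideline does not impose a fixed number of pupils per class. If it did, the analyst would already have the number of pupils present (covariate X.5) to judge whether class size matters.

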1. iHWWS rates (impact evaluation, RQ1)	iHHWS after toilet use observations in classroom (treatment & control)	4 months post- implementation	Enumerators will observe whether pupils wash their hands with soap, wash without soap, or do not wash, after they have used classroom toilets. This will be used to estimate the causal impact of the nudges intervention on iHHWS rates.
2. Homogeneity in toilet and handwashing environment (impact evaluation, RQ1)	Structured facilities observations for both treatment and control (treatment & control)	4 months post- implementation	Structured observations of each facility will assess factors such as: presence of existing WASH-related informational posters, whether the handwashing area is used for other non-WASH purposes (e.g. storage, dish-washing area), whether the handwashing station has objects unrelated to handwashing ³³ , how many primary colors are present in health corner where handwashing station is present, and other factors related to visual clutter to be finetuned after piloting. These will be used to construct a measure of whether the facility is conducive to nudges, to be used in subgroup analyses.
2. Access to soap and water (impact evaluation, RQ2)	Structured facilities observations (Treatment & control)	4 months post- implementation	Structured observations of whether classroom handwashing facilities including soap and water. These will be used to estimate the causal impact of the nudges intervention on pupil access to soap.
3. Nudges implementation (process evaluation, RQ3)	Structured facilities observations (treatment)	During implementation visit but after nudge installations are completed	Structured observations of facility after implementation, to assess presence and condition of nudges in toilet and/or handwashing station. These will be used to assess if installation proceeded as intended.
4. Nudges implementation (process evaluation, RQ3)	Structured facilities observations (treatment)	4 months post- implementation	Structured observations of presence and condition of nudges in toilets and/or handwashing facilities. These will be used to assess if installed nudges functioned and lasted as expected.

³³ A concern is that handwashing areas both across and within schools may differ in terms of how conducive they are to nudges; more cluttered and busy environments may dilute the impact of nudges.

Pre-analysis plan [DRAFT] | January 20, 2020

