4. TECHNICAL RISKS AND MITIGATION STRATEGIES

"Clutteredness" in school handwashing environment

Schools in our sample may differ in terms of baseline toilet and handwashing facility environments. A potential concern is that among handwashing areas that are cluttered and busy, all nudges by the handwashing area (footpath, arrow sticker, eye sticker) would be less likely to grab attention by producing the necessary element of surprise; therefore, any potential impact of the intervention may be diluted. This is particularly likely if the bathrooms already have existing WASH-related informational posters, are crowded with other features (e.g. cabinets or items for storage), or used for other purposes such as tooth-brushing or cleaning dishes. Since we hypothesize that baseline bathroom "clutteredness" factors like these mediate the impact of nudges, substantial differences in the toilet/handwashing environment present the risk of reducing the impact of nudges overall. If the average school is very cluttered, we may not have a large enough sample size to estimate the differential effects of the nudges in cluttered schools and uncluttered schools.

We address this risk in two ways:

1) During school sampling, we prioritized selecting schools with "nudge enabling" handwashing environments, based on characteristics available in the OMS data which we hypothesized could reflect conduciveness to nudges. This is described in Section 2.5 Recruitment of Participants (Sampling).

2) Given that OMS data is at the school-level and there may be difference within a school in terms of handwashing facilities, during our endline data collection, we will also collect detailed information on toilet and handwashing facility environment. Using this data, we will explicitly model for heterogeneity of "nudge enabling" environments in our analysis of the impact of nudges.

Observer effects and social desirability bias

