Class	Number of pupils in the classroom	X.5 – continuous variable where value represents the number of pupils present in the classroom during the observation period	Classroom size may be associated with school resources and teacher quality or attention, which may influence pupil opportunity and incentives to wash hands with soap. Further, if handwashing with soap after toilet use is considered to be a norm (or habit) that the nudges remind pupils of, and if the class is considered as the primary 'social unit' for this norm, the number of pupils in this social unit may influence the likelihood of the norm arising and persisting.

Table 4: Control Variables for Research Question 1

³⁷ This variable may be converted to an ordinal variable to mitigate random error due to imprecision in the number of pupils reported.

³⁸ See Table 7 in the *Sampling* section of the evaluation design document for a description of 11 indicators an additional information on the online monitoring system (OMS) Evaluation Design Document

Pre-analysis plan [DRAFT] | January 20, 2020

	Nudge- conducive	X.6 - Binary variable indicating whether the handwashing area location near/in the classroom is "nudge conducive"	Nudge-conducive handwashing areas are those with combinations of features that indicate they may be more conducive to nudge intervention than handwashing areas without those features. Please see Section 3.2 Data Collection Activities for details of these nudge-conducive features. The nudge intervention may have greater impact for nudge-conducive handwashing areas than non-nudge conducive areas.
Unit	Co-variate	Metric	Hypothesized relationship to outcome
Pupil	Gender	X.7 – binary variable for whether pupil observed is female	Traditional gender roles tend to involve more tasks that may require handwashing for girls than boys, such as cooking or cleaning, and may thus facilitate building handwashing habits among girls.
	Grade	X.8 – categorical variable where each	The behavioral nudges targeted at changing pupil behavior may be more engaging and/or effectively

1.c. Analytic model

Specification for LPM: The effect of the treatment on the outcome variables listed in **Error! R** eference source not found. for which the analytic model indicated is the Linear Probability Model will be measured by conducting the following regression:

$$Y_{ij} = \beta_0 + \beta_1 T_j + \overrightarrow{\beta_2} \vec{X}_{2ij} + \varepsilon_{ij}$$

Where:

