 $^{^{\}rm 39}$ Observations in which the student grade was unknown will be excluded.

Pre-analysis plan [DRAFT] | January 20, 2020

1.d.iv. Treatment impact by WinS implementation quality index score: In order to compare the average effect of the nudges intervention on the outcome of independent handwashing after toilet use across different levels of WinS implementation quality, sub-group analysis will be conducted using the following regression:

$$Y_{ij} = \beta_0 + \beta_1 T_j + \beta_2 W_j + \beta_3 (T_j \times W_j) + \overrightarrow{\beta_4} \overrightarrow{X}_{4ij} + \varepsilon_{ij}$$

Where:

- *W_j* is an ordinal variable between 0 and 11 denoting the WinS implementation quality index score for school *j*
- \vec{X}_{4ij} represents a vector of pupil, school, and class level co-variates as specified in Table 2, excluding WinS implementation quality index score
- All other regression terms are defined as they were in the previous regression specification and β₃ is the coefficient of interest.

1.d.v. Treatment impact by nudge conduciveness: In order to compare the average effect of the nudges intervention on the outcome of independent handwashing after toilet use depending on the context's conduciveness to nudges, sub-group analysis will be conducted using the following regression:

Where:

$$Y_{ij} = \beta_0 + \beta_1 T_j + \beta_2 W_j + \beta_3 (T_j \times N_i) + \beta_4 X_{4ij} + \varepsilon_{ij}$$

- N_i will be a binary variable (to be constructed after seeing the distribution) =1 if the pupil
 was exposed to a nudge-conducive handwashing environment at the time of toiet use and
 =0 if not
- \vec{X}_{4ij} represents a vector of pupil, school, and class level co-variates as specified in Table 2, excluding WinS implementation quality index score
- All other regression terms are defined as they were in the previous regression specification and β₃ is the coefficient of interest.

1.e. Presentation of results: a regression table will be included for each specification to describe the correlation between key indicators of interest and co-variates. Data visualizations describing the level of the outcomes variables in the treatment and control group may also be included.

RESEARCH QUESTION 2

2.a Research question 2: What is the causal impact of the behavioral nudge intervention on pupil access to handwashing facilities with soap and water?

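### The nudge-conducive flag (X.6 / N_i) stands for baseline clutter but is scored after installation, with no rule leaving the nudges out of the score; the subgroup test in 1.d.v bears most of the risk

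*SAP*

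**What the plan says.** **Concept.** SAP Section 4 introduces clutter as a pre-existing condition: "Schools in our sample may differ in terms of baseline toilet and handwashing facility environments". It expects that in cluttered areas "all nudges by the handwashing area (footpath, arrow sticker, eye sticker) would be less likely to grab attention". Section 2.6 likewise names the baseline handwashing environment as what changes the nudge effect. It declines to compare nudge-enabled with other schools and relies on facility-level clutter instead.

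**Timing.** Section 2.5 rules out a baseline round. Section 4 says "during our endline data collection, we will also collect detailed information on toilet and handwashing facility environment", and Section 3.2, Table 2 places this 4 months after implementation in both arms. The installation-visit observation covers treatment schools only and records the presence and condition of nudges, so it gives no baseline clutter measure.

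**Items.** Table 2 lists existing WASH posters, non-WASH use of the area, objects not related to handwashing, and "how many primary colors are present in health corner where handwashing station is present". The list is then left open, with a closing reference to "other factors related to visual clutter to be finetuned after piloting".

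**Use.** Table 4 lists "X.6 - Binary variable indicating whether the handwashing area location near/in the classroom is" nudge-conducive, so the flag enters the covariate vector X_2ij of the main RQ1 model (1.c). In 1.d.v, N_i "will be a binary variable (to be constructed after seeing the distribution" is known, and its interaction with treatment is the coefficient of interest. Table 6 counts this as one of four subgroup tests under the Holm correction. Section 6, 1.b says estimates will be reported with and without controls.

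**The concern.** Section 1.2.1 describes a colourful footprint path to the handwashing station, an eye sticker above it and an arrow by the soap dish. Only treated schools receive these. If an enumerator counts colours or visual clutter with the nudges in view, a room that would have been conducive at baseline may be scored otherwise, in the treated arm only. N_i = 1 would then select different kinds of room in the two arms, and the T x N_i contrast would no longer compare like with like.

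This matters because 1.d.v is the planned test of where nudges work, and Section 2.6 says that conducive environments would be the target of any scale-up. A lesser issue is that X.6 is a post-installation variable used as a control in the main RQ1 model.

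**Working it through.** **Inputs from the SAP (Section 2.5):** control rate 10%, effect 7 pp (10% vs 17%), ICC 0.1, 26 pupils per school, 66 schools per arm, two-sided alpha 0.05 (sidedness assumed).

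**The SAP's own figure.** 373 pupils per arm before clustering; design effect 1 + 25 x 0.1 = 3.5; 373 x 3.5 / 26 = 50.2 schools per arm. This agrees with the stated 100 schools, and nothing here changes it.

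**Standard error of the unadjusted effect, 66 schools per arm.** sqrt[(0.10 x 0.90 + 0.17 x 0.83) x 3.5 / (66 x 26)] = sqrt[0.2311 x 3.5 / 1716] = 2.17 pp.

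**Assumptions not in the SAP:** half of rooms truly conducive; average effect 7.0 pp; effect 4 pp larger in conducive rooms (d = 4); no gap between room types in the control arm (g = 0); a share f of truly conducive treated rooms scored as non-conducive.

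**Interaction.** Treated rooms scored conducive are all truly conducive. Those scored non-conducive are a mix in the ratio f : 1. The treated-arm contrast is therefore (g + d)/(1 + f). Subtracting the control contrast gives T x N = (g + d)/(1 + f) - g.

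**Adjusted main effect.** 7.0 - b x (difference in mean N between arms), where b is the within-arm slope on N, weighted by the within-arm variance of N. For f = 60%:
- Treated share conducive: 0.5 x 0.4 = 0.20, variance 0.16. Control variance: 0.25.
- b = (0.16 x 2.50 + 0.25 x 0)/0.41 = 0.976.
- Adjusted effect = 7.0 + 0.976 x 0.30 = 7.29 pp.

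| f | T x N (true 4.0) | Adjusted main effect | Same, re-scored the other way |
|---|---|---|---|
| 0% | 4.00 | 7.00 | 7.00 |
| 10% | 3.64 | 7.09 | 6.91 |
| 20% | 3.33 | 7.16 | 6.84 |
| 40% | 2.86 | 7.26 | 6.74 |
| 60% | 2.50 | 7.29 | 6.71 |

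The interaction shrinks in the same way in either direction of re-scoring. The largest main-effect shift, 0.29 pp, is 0.29/2.17 = 0.13 of a standard error. With 30% or 70% of rooms conducive, the interaction reads 3.84-1.67 pp and the main effect moves by at most 0.34 pp. The unadjusted effect stays at 7.0 pp because N does not enter it.

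**Sensitivity: a gap between control rooms.** Take g = 4 and d = 0. With half of rooms of each kind, this is the largest gap possible at the roughly 2% rate of the previous study (0% vs 4%). T x N then reads -0.36 to -1.50 pp where the truth is zero, and the adjusted effect is 7.19-8.02 pp (6.81-5.98 pp in reverse). Table 4 does not posit such a gap: its stated reason for X.6 is a larger nudge effect in conducive areas.

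**The case against.** **The exclusion rule may yet be written.** Section 3.2 defers enumerator procedures to Data Collection Guidelines not yet created, and the items are to be refined after piloting in schools that also hosted the nudge-installation pilot. Nudge presence has its own endline fields under RQ3. This stands as a reason not to say that rooms will be mis-scored. It does not supply the rule.

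**Most named items are protected.** The poster, object and non-WASH-use items largely leave nudges out by their wording. This stands. What remains is the colour count and the unwritten clutter items.

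**Nothing shows that re-scoring will occur.** No passage says that the nudges add a primary colour not already present, or how the count is weighted. This stands. The share is assumed and may be zero.

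**The test is weak in any case.** In simulations (132 schools, 26 pupils, ICC 0.1, 6 rooms per school assumed), a true 4 pp interaction is detected 10-16% of the time at the strictest Holm step (0.05/4 = 0.0125) with no re-scoring, and about 4% at f = 60%. This stands too: re-scoring makes a weak test weaker.

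**Stronger readings that the text does not support.**
- A reader might infer from the printed 1.d.v equation, which has beta_2 W_j where one expects N_i, that the main effect of N is missing, so that a 4 pp control gap alone would appear as a 4.0 pp interaction. On the natural reading it is not missing. W_j enters explicitly, so X_4ij rightly appears "excluding WinS implementation quality index score". X.6 is not excluded, so it remains in X_4ij once the reference to Table 2 is read as Table 4. The interaction then reads 0.0 pp in that case.
- A reader might also take the post-hoc cut-off as chosen on outcomes. The text refers only to a distribution, most naturally that of the index itself. That is missing detail, not evidence of selection.

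**Conclusion.** The point holds as a correctable weakness in how the flag is scored and used. A variable meant to represent baseline clutter is measured after installation, partly on features the nudges can alter, with no stated exclusion. The exposure is mainly in 1.d.v: under the illustrative assumptions, a true 4.0 pp interaction reads 3.64-2.50 pp for re-scoring shares of 10-60%, and is unbiased if nothing is re-scored.

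A reader might infer that the trial's main result is compromised. The documents do not support that. Under the SAP's own hypothesis the with-controls RQ1 estimate moves by about 0.3 pp at most, a small fraction of its 2.17 pp standard error, and the no-controls estimate, which will also be reported, is untouched. Nor is a raised false-positive rate claimed for 1.d.v.

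The change is worth making because it costs little and must precede scoring: nudge material already counted may not be separable afterwards.

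**What to change.** 1. Drop X.6 from X_2ij in the main RQ1 models. The school-level nudge-enabled indicator X.4, built from OMS data for sampling, can stay.
2. Build N_i only from features the nudges cannot alter, or state in the SAP and the Data Collection Guidelines that installed nudges are left out of every colour, poster and object count. Tabulate N_i by arm so that any imbalance shows.
3. As tidying only, with no bias implied: in 1.d.v write N_i explicitly as a main effect, cite Table 4 rather than Table 2, and state that X_4ij then omits X.6.

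The cost is a few words in Table 4 and 1.d.v and one line in guidelines still to be written. The downside is one fewer control in the main model and possibly a thinner index. The sample size does not change.
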